7.1 Study Schedule of Events	
7.2 Blood Collection Schedule	

1. Objectives

We hypothesize that IMM-124E, a bovine colostrum enriched with anti-LPS antibodies, will improve insulin resistance and decrease systemic and hepatic inflammation through modulation of bacterial products and the microbiome in pediatric NAFLD.

1.1 Primary Objective: The principal objective of this blinded, placebo-controlled, pilot study is to evaluate whether 12 weeks of IMM-124E in children with NAFLD in combination with standard of care (SOC) will decrease inflammation in the liver as measured by ALT. Specifically, percent change in ALT from Week 0 to Week 12 in treatment compared to placebo.

1.2 Secondary Objectives:

- To assess the safety and tolerability of IMM-124E in children with NAFLD
- To assess the effects of IMM-124E on secondary and exploratory endpoints:
 - Mean change in ALT in treatment group compared to placebo
 - Fasting glucose and insulin
 - Hemoglobin A1C
 - o Adipo-IR
 - Oral glucose tolerance test
 - NAFLD pediatric diagnostic panel
 - Fasting plasma lipids
 - Stool microbiome
 - Blood transcriptomics
 - Systemic inflammation (cytokines)
 - Metabolomics
 - Visceral Adiposity (AMRA MRI scan)
 - Hepatic fat percent (AMRA MRI scan)
 - o BMI z-score
 - Waist circumference
 - Depression
 - Quality of life
 - Composite endpoint of "metabolic improvement" specified as > 10% improvement in TG/HDL ratio, improvement in insulin resistance, and >10% improvement in ALT

2. Background and Significance

Nonalcoholic fatty liver disease (NAFLD) is an aggressive, obesity-associated chronic liver disease that affects ~7 million children in the US (10% of all children) and is one of the top 3 indications for liver transplant in adults. Currently, the only treatment available for NAFLD is lifestyle advice to decrease adiposity and improve insulin sensitivity but this is rarely effective. It is our long term goal to improve the health of children by understanding how to prevent, treat and cure NAFLD. In our previous studies, we demonstrated that children with NAFLD have endotoxemia as well as systemic inflammation. Further, individuals with NAFLD have a disturbed microbiome (dysbiosis) and increased gut permeability. Thus, the mechanism of NAFLD is thought to include chronic inflammation from intestinal microbiome-derived

products (lipopolysaccharide (LPS) and metabolites) which pass through the "leaky gut" to the liver where they activate the innate immune response.

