children and found that endotoxin levels rise immediately postprandially in NAFLD while in obese and normal weight children they do not¹⁰. Increased endotoxin results from a combination of altered microbiota composition (dysbiosis) and increased gut permeability from disruption of tight junctions, thus allowing increased movement of microbial products from the lumen into the portal blood stream into the liver (reviewed in¹¹ Figure 1). Supporting this, pediatric NAFLD studies have shown increased Gammaproteobacteria and *Prevotella* as well as increased energy production by the microbiota¹². There is growing consensus that treatment for NAFLD at the intraluminal level is needed¹²⁻¹⁶.

Why use IMM-124E to treat pediatric NAFLD? In a mouse model of extreme obesity, treatment with anti-LPS enhanced bovine colostrum (similar to IMM-124E) led to decreases in IR, alanine amino transferase (ALT) levels and serum triglycerides when compared to control mice, and decreases in serum TNFα levels¹⁹. IMM-124E was used to treat 10 adults with biopsy-proven NASH for 30 days in an open-label pilot study¹⁸. IR improved in all participants and an improved lipid profile and liver enzymes was seen in 5 out of 10. There are two active trials using IMM-124E reported on clinicaltrials.gov. One is a 30 day RCT treating patients with alcoholic hepatitis sponsored by the NIH and the other is an industry sponsored phase II study of IMM-124E for patients with NASH. Bovine colostrum has been well-tolerated in previous studies. The most common adverse events are nausea, abdominal pain, flatus and/or diarrhea and all are rare.

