5.2 Secondary Endpoints

Secondary efficacy-related outcomes will include change in: GGT, fasting glucose and insulin, total body insulin sensitivity (OGTT), BMI z-score, waist circumference, and quality of life. Safety-related outcomes will include: sex hormones, proportion of participants with nausea, emesis, diarrhea, and any other adverse event, PROMIS, body fat by MRI, hepatic fat by MRI, and change in metabolic state.

5.3 Power Analysis:

A typical group of patients with NAFLD have a mean ALT level of $130 \pm 63 \text{ U/L}^{10}$. In the TONIC treatment study of children with NAFLD, there was a -20 ± 10 U/L and -30 ± 8 U/L change (average of 15% – 23% change) in ALT in treatment groups respectively and no change in ALT with placebo at 12 weeks⁶. A sample size of 11 participant per group is required to achieve a least 90% power to detect a 15% point difference in the average % change in ALT from baseline to week 12 between the two groups. Sample size was calculated assuming common standard deviation of 10% using a two-sided Mann-Whitney tests with a 0.05 significance level.

5.4 Statistical Analysis:

Primary Outcome Analysis:

Change in ALT from baseline to week 12 will be converted to a % change from baseline to account for the wide range of ALT values expected at baseline. A Mann-Whitney U test will be used to compare the percentage change in ALT among the two intervention groups. Data will be described as mean or median percent change, as appropriate.

General Statistical Considerations:

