With multiple follow-ups, longitudinal data will be available, and these repeated measures are likely to be correlated (i.e., weight, PROMIS measures, BMI-score, etc.). The analysis of repeated measures data is needed that properly accounts for the correlation between multiple observations from the same participant. Mixed effects models, accounting for the longitudinal measures, will be summarized with adjusted means and 95% confidence intervals for continuous outcomes. For categorical outcomes, we will apply generalized linear mixed models with appropriate distribution and link functions. In these models, the statistical test for interaction between time on study and intervention group will be the primary overall hypothesis to test to determine whether an outcomes in the two study groups changed in significantly different ways during follow-up (i.e., different temporal patterns over time). For significant interactions, post-hoc tests will be used to compare differences in the least square means at each time point in each intervention arm. All statistical tests will be two-sided and unadjusted for multiple comparisons due to the pilot nature of this trial.

Missing Data: A potential problem in any of the proposed analyses is missing data, which can cause the usual statistical analysis of complete available data to be subject to bias. Every effort will be made to minimize missing data on outcomes and covariates, and we will encourage patients that drop out of a study to return for final follow-up testing even if they missed previous scheduled evaluations.

Sensitivity Analysis: A sensitivity analysis will be performed by examining the effect of compliance (i.e., number of doses taken) on the primary and secondary endpoints.

5.5 Data Storage & Sharing:

Hard copy data will be entered by the study coordinators. All data will be stored in a REDCap database. Only study personnel (PI, Co-I's study coordinators, research assistants etc.) will have access to identifiable data. Data will be de-identified before analysis. Data will be stored in locked research material cabinets and in password-secured on the Emory network.

De-identified data will be shared with Immuron Ltd. and a sub-set of de-identified data will further be shared with Advanced MR Analytics AB (AMRA) who is providing imaging analysis services for the study.

5.6. Sample storage:

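### Section 5.4's only test for categorical outcomes is a time-by-arm interaction, which does not compare the per-child adverse-event proportions between arms and has nothing to test in the composite

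*Combined protocol and SAP*

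**What the plan says.** The method is in section 5.4, General Statistical Considerations, in the paragraph on longitudinal data. That paragraph starts from the point that "these repeated measures are likely to be correlated (i.e., weight, PROMIS measures, BMI-score, etc". It then sets mixed models for continuous outcomes and adds: "For categorical outcomes, we will apply generalized linear mixed models with appropriate distribution and link functions". The main test follows: "In these models, the statistical test for interaction between time on study and intervention group will be the primary overall hypothesis to test". Comparisons at individual visits come after it: "For significant interactions, post-hoc tests will be used to compare differences in the least square means at each time point in each intervention arm".

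No other inferential method for a yes/no outcome appears. The t-test and Mann-Whitney test are for percent change, and mixed models or ANCOVA are for absolute change. Counts and percentages are offered only to describe the cohort and subgroups.

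Two kinds of outcome in the plan are clearly categorical:

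- Section 5.2 lists, among the safety outcomes, the "proportion of participants with nausea, emesis, diarrhea, and any other adverse event".
- Section 1.2 lists a "Composite endpoint of 'metabolic improvement' specified as > 10% improvement in TG/HDL ratio, improvement in insulin resistance, and >10% improvement in ALT".

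On expected frequency, section 2 says only this: "The most common adverse events are nausea, abdominal pain, flatus and/or diarrhea and all are rare". No rate is given.

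**The concern.** A time-by-arm interaction asks whether the arms follow different patterns over time. The safety question is whether more children on IMM-124E than on placebo have an event. If the product raises event risk by a similar amount in both six-week periods, the arms differ but the difference does not change between visits, so the interaction is null. The contrasts that could show the difference are described only after that interaction is significant.

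Safety and tolerability is the first-listed secondary objective in section 1.2 and part of the first aim in section 2, which also says the product has not yet been tested in children. The trial is meant to inform a larger multicenter one. Section 3.6 notes that the placebo contains more lactose, so gastrointestinal events may occur in both arms. Arm-specific proportions with intervals are needed to interpret any comparison, and none are specified.

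**Working it through.** **Inputs from the plan.** 20 children per arm (synopsis, Sample Size); two-sided tests without multiplicity adjustment (5.4); visits at Weeks 6 and 12 (4.3); adverse-event review at baseline, Week 6 and Week 12 (Attachment 1).

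**Assumptions.** All event rates, and a random-intercept SD of 1 on the logit scale. The plan gives neither.

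**The plan's own figure.** The only sample-size figure is 11 per group for percent change in ALT (15-point difference, SD 10%). Simulated Mann-Whitney power is 89.9% at 11 per arm, so it reproduces. It is unaffected by this point, and no figure is given for a categorical outcome.

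**Step 1: what the interaction measures.** With two post-baseline visits the interaction is

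[logit p(IMM, W12) − logit p(IMM, W6)] − [logit p(placebo, W12) − logit p(placebo, W6)].

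Take 25% against 5% at both visits: logit 0.25 = −1.10 and logit 0.05 = −2.94, a gap of 1.84 each time. Both brackets are 0, so the interaction is 0 although the risk is five times higher.

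**Step 2: rejection rates for a steady excess, Weeks 6 and 12 only.** Each simulated trial was analysed by a random-intercept logistic model with a likelihood-ratio test of the interaction, and by Fisher's exact test on ever/never per child. Runs per row: 400 for the first three, 500 for the last three.

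| Per-visit risk, placebo v IMM-124E | Interaction test | Fisher, ever/never |
|---|---|---|
| 3% v 20% | 6% | 56% |
| 5% v 30% | 8% | 74% |
| 5% v 40% | 5.5% | 94% |
| 5% v 25% | 5.6% | 56% |
| 10% v 40% | 6.0% | 73% |
| 10% v 50% | 6.6% | 86% |

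The interaction column is close to the 5% false-positive rate. Monte Carlo error at 500 runs is √(0.05 × 0.95/500) ≈ 1 point.

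**Step 3: with a baseline row** (2-df interaction test, 300 runs, the last three scenarios above). With no events at baseline the test rejects in 1.7% to 4.0% of trials. With a 5% background rate at baseline it rejects in 20% to 31%. The plan does not say how time would be coded.

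**Step 4: low event rates.** If the rates are per-child totals rather than per-visit risks, exact Fisher power at 20 per arm is:

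- 30% for 5% v 25%, 49% for 10% v 40%, and 74% for 10% v 50%;
- 0.2% for 1% v 5%, 3% for 2% v 10%, and 7% for 5% v 15%.

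At rates that could fairly be called rare, no test is useful.

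**Step 5: zero counts.** P(no events among 20) = (1 − p)^20:

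| True rate p | P(zero in one arm) |
|---|---|
| 1% | 82% |
| 2% | 67% |
| 5% | 36% |
| 10% | 12% |
| 15% | 4% |
| 20% | 1% |

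With a zero count the log-odds estimate is not finite and Wald tests fail; a likelihood-ratio statistic stays finite. Fisher's test remains defined: 0/20 v 5/20 gives p = 0.047 and 0/20 v 4/20 gives p = 0.106. The exact two-sided 95% upper limit for 0/20 is 1 − 0.025^(1/20) = 16.8%.

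**Step 6: the composite.** It is defined by improvement, so it has no baseline value. Attachment 1 schedules the OGTT only at baseline and Week 12, and section 3.9 places fasting only before those two visits. The composite therefore appears to be one Week 12 yes/no per child. With one time point there is no time factor and no interaction.

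**The case against.** The strongest reply is about scope. The paragraph concerns repeated measures and names neither adverse events nor the composite, so it may have been meant only for categorical outcomes that are repeated. A reader might infer that the plan expressly assigns the adverse-event proportions to the interaction test; it does not. But on the narrow reading the plan has no inferential method for these outcomes, and the sentence has little else to govern. Either way the same text is missing.

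A reader might also infer that the test can see no excess at all. That is too strong. Adverse events are reviewed at baseline (4.1, Attachment 1) and documented from consent (4.10), so a pre-treatment level can exist, and Step 3 then gives 20% to 31%.

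That the model breaks down is also too strong as a general claim. Zero counts are common at rates of 5% or below and uncommon at 15% to 20%, and the failure concerns Wald estimates.

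The steady-excess argument does not carry over to the composite, whose problem is the absence of a time factor.

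Two further objections stand in part. The simulation needs two values per child, while section 5.2 defines one; taken literally, the adverse-event proportion also has no interaction to test, so Step 2 shows what happens if the rule is applied by splitting events by visit. And the large advantage for Fisher's test depends on event rates well above rare.

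Finally, a reader might infer that a large excess would go unnoticed. The DSMB receives adverse-event data (3.12, 4.10), so the documents do not support that. Its review protects participants but does not define the final between-arm comparison.

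**Conclusion.** The point holds in a limited form. The only inferential rule for categorical outcomes tests the wrong quantity for adverse-event proportions and does not fit the composite.

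For a steady excess of the sizes assumed, the interaction test rejects in about 5% to 8% of trials over Weeks 6 and 12, and in 20% to 31% with a baseline row and a 5% background rate. Fisher's test rejects in 56% or more on the two-visit data. These figures rest on assumed event rates and a random-intercept SD of 1. At truly rare rates neither test has useful power and the intervals carry the information.

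The primary ALT analysis and its sample size are not affected. The change should be made because safety is a stated objective and the remedy is simple.

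**What to change.** In section 5.4, add a short paragraph for per-participant binary outcomes, covering each treatment-emergent adverse-event proportion and the composite:

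- Compare arms with Fisher's exact test, or an exact test stratified by the randomisation age group (6–12 and 13–19 years).
- Report the risk difference with a 95% CI.
- Report each arm's proportion with a Clopper-Pearson interval, including the upper limit when the count is zero (16.8% for 0/20).
- State that the composite is assessed once, at Week 12, if that is the intent.

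Keep GLMMs for categorical outcomes that are measured repeatedly. The cost is wording only, with no new data or visits. The small downside is that Fisher's test is slightly conservative.

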	improvement in TG/HDL ratio, improvement in insulin resistance, and >10%		
	improvement in ALT		
Study Duration (per	Up to 19 weeks total		
participant):	• Up to 6 weeks screening		
	12 week treatment		
Study Duration (calendar	• Study start-up: 0 – 4 months		
time):	Recruitment phase: 5 -14 months		
	Follow-up phase: 15 - 18 months		
Math Cale a duile :	Analysis and reporting: 18 - 24 months		
Visit Schedule:	Screening Visit		
	Baseline visit		
	Follow up visits		
Ctatistical Analysis	• Week 6 and Week 12 visits		
Statistical Analysis:	Descriptive variables of the cohort and subgroups will be analyzed using means and standard deviations or medians and ranges, as appropriate. Percent change in		
	primary and secondary outcomes will be compared using two sample t-test or		
	Mann-Whitney test. Absolute change over time will be compared using mixed		
	model or analysis of covariance.		
Sample Size:	A sample size of 11 participant per group is required to achieve a least 90% power		
Sample Size.	to detect a 15% point difference in the average % change in ALT from baseline to		
	week 12 between the two groups. Sample size was calculated assuming common		
	standard deviation of 10% using a two-sided Mann-Whitney tests with a 0.05		
	significance level. We will include 20 participants per group to allow for drop out,		
	intra-individual variability and multiple hypothesis testing.		
Safety Monitoring:	A DSMB will monitor the data for safety and efficacy for outcomes such as nausea,		
earcey monitoring.	abdominal pain, flatus, diarrhea, pregnancy, hepatotoxicity and any other outcomes		
	or events identified as safety related.		

Table of Contents

1.1 Primary Objectives71.2 Secondary Objectives72. Background & Significance73. Study Design113.1 Design Overview113.2 Inclusion Criteria113.3 Exclusion Criteria113.4 Rescreening123.5 Treatment Groups123.6 IMM-124E Administration123.7 Recruitment and Retention133.8 Sources and Materials133.9 Potential Risks133.10 Protection Against Risks143.11 Potential Benefits153.12 Data and Safety Monitoring164. Study Plan16
2. Background & Significance.73. Study Design.113.1 Design Overview.113.2 Inclusion Criteria.113.3 Exclusion Criteria.113.4 Rescreening.123.5 Treatment Groups.123.6 IMM-124E Administration.123.7 Recruitment and Retention.133.8 Sources and Materials.133.9 Potential Risks.133.10 Protection Against Risks.143.11 Potential Benefits.153.12 Data and Safety Monitoring.16

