- Urine pregnancy test for females of childbearing potential
- Blood spot collection
- MRI (Brief scan for full body and liver fat assessment)

• Optional Sub-study: Accelerometer data collection for 1 week

4.2 Randomization Procedures:

After consent and eligibility for the trial is confirmed, participants will be randomly assigned to either IMM-124E or placebo. The randomization will be assigned by the research pharmacist and will be blocked by age group (6-12 years versus 13-19 years) to ensure balanced groups. The investigators, lab personnel, research coordinators and participants will be blinded to the assignment. The research pharmacy will dispense the similarly appearing IMM-124E and placebo at baseline and again at Week 6.

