Analysis of primary and secondary outcomes will be performed using an intention to treat analysis. Descriptive variables of the cohort and subgroups will be analyzed using means and standard deviations, medians and ranges, or counts and percentages, as appropriate. For secondary measures, absolute change over time will be compared using mixed models or analysis of covariance. We will test the data to evaluate underlying model assumptions (i.e., normality, homoscedasticity). If these assumptions are not met, then we will attempt to transform the data. Standard transformations of the response variable such as the log, square root and Box-Cox transformations will be examined. If data transformation is inadequate to meet the analysis assumptions, then rank transformation of the data will be performed and the rank transformed response variables will be analyzed and reported. In situations where covariates could potentially have an effect on the response variable, we will add covariates to adjust for subgroup effects. Underlying model assumptions will be tested (such as homogeneity of slopes across exposure groups). Standard regression criteria will be used to assess appropriateness of including particular covariates. Collinearities will be reduced in multivariable modeling through the careful initial assessment of correlations and the avoidance of redundancies in candidate covariates.

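### Repeated secondary outcomes are tested by a time-by-arm interaction; a Week 12 arm difference adjusted for baseline and age stratum would be a better main result at almost no cost

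*Combined protocol and SAP*

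**What the plan says.** Three places in the combined protocol and SAP bear on how continuous secondary outcomes are analysed.

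- **Synopsis, Statistical Analysis.** Percent changes in "primary and secondary outcomes will be compared using two sample t-test or" a Mann-Whitney test. Absolute change over time goes to a mixed model or analysis of covariance.
- **Section 5.4, General Statistical Considerations.** "For secondary measures, absolute change over time will be compared using mixed models or analysis of covariance". On adjustment: "In situations where covariates could potentially have an effect on the response variable, we will add covariates to adjust for subgroup effects". Which covariates enter is left to standard regression criteria.
- **Section 5.4, on repeated measures.** In the mixed models "the statistical test for interaction between time on study and intervention group will be the primary overall hypothesis to test". Then: "For significant interactions, post-hoc tests will be used to compare differences in the least square means at each time point in each intervention arm". The models "will be summarized with adjusted means and 95% confidence intervals for continuous outcomes".

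Week 12 is fixed in the analysis text only for the primary endpoint, percent change in ALT, which has its own Mann-Whitney test. Section 4.2 says that randomisation is "blocked by age group (6-12 years versus 13-19 years) to ensure balanced groups", but Section 5.4 does not mention age group.

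The schedules in Attachments 7.1 and 7.2 give Week 0, 6 and 12 values for weight, height, waist and the metabolic panel. PROMIS, the glucose tolerance test and MRI are done at Weeks 0 and 12 only.

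**The concern.** The trial asks whether 12 weeks of treatment changes the outcome. An interaction test asks whether the two arms follow different paths over the visits. With three visits and categorical time, it spreads its power over two degrees of freedom. It gives a p-value and not an end-of-treatment difference, and it does not use the baseline value as a covariate.

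This matters because Section 5.1 says that if the primary outcome is missed but important secondary markers are met, the result will support the design of future studies. A later design needs a Week 12 difference with an interval. The plan does not commit to one for these outcomes, and the three places listed above allow different main tests without saying which governs.

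**Working it through.** **The plan's own figure.** The only sample-size figure is 11 per group for the primary outcome (15-point difference, SD 10%, 90% power, Mann-Whitney). It reproduces: the normal formula gives 10 per group, and 10 / 0.955 = 10.5, so 11. No figure is given for the secondary mixed models, so the check below is comparative.

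**Reading the interaction.** Section 5.4 does not state outright whether Week 0 is a response or a covariate, or how time is coded. Two clues point the same way.

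- It says "these repeated measures are likely to be correlated (i.e., weight, PROMIS measures, BMI-score, etc", yet PROMIS has only Weeks 0 and 12. With Week 0 as a covariate, PROMIS would have one response per child and no time-by-arm interaction would exist.
- The follow-up tests compare means at each time point, which suggests categorical time.

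The natural reading is therefore Week 0 as a response level with categorical time.

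**Assumptions (not in the documents).** Equal variances, the same correlation r between any two visits, complete data, no arm difference at Week 0, two-sided 5%. The effect is scaled so that the baseline-adjusted Week 12 contrast has 80% power, that is, noncentrality (nc) 7.849. The gain from adjusting for age stratum is not counted.

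**Formulas.** In units of the visit variance:

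- Baseline-adjusted Week 12 value: variance factor 1 - r².
- Unadjusted Week 12 change: variance factor 2(1 - r). So nc = 7.849(1 - r²) / [2(1 - r)] = 7.849(1 + r)/2, on 1 df. With two visits, this is the interaction test.
- Three-visit interaction, 2 df: nc = 7.849(1 - r²) v'S⁻¹v, where v is the effect at Weeks 6 and 12 and S = (1 - r)[[2,1],[1,2]].
  - Steady effect, v = (1, 1): nc = 7.849 × 2(1 + r)/3.
  - Gradual effect, v = (0.5, 1): nc = 7.849(1 + r)/2. This equals the nc of the change test, but is spent on 2 df.

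Example, r = 0.5: steady 7.849 × 2 × 1.5/3 = 7.85; gradual and change 7.849 × 1.5/2 = 5.89.

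| r | Three visits, steady (2 df) | Three visits, gradual (2 df) | Two visits (1 df) | Adjusted Week 12 |
|---|---|---|---|---|
| 0.50 | 70.9% | 57.5% | 68.0% | 80% |
| 0.65 | 75.2% | 61.9% | 72.1% | 80% |
| 0.80 | 79.0% | 66.0% | 75.7% | 80% |
| 0.90 | 81.3% | 68.5% | 78.0% | 80% |
| 0.95 | 82.4% | 69.7% | 79.0% | 80% |

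**Small-sample check.** Simulation at 20 per arm (80,000 runs per cell, r = 0.5/0.65/0.8, effect set so that ANCOVA has 80%) gives 72.7/76.3/80.9% for steady, 59.4/63.2/67.8% for gradual and 69.1/72.8/77.0% for the unadjusted change t-test. Rejection under the null is 4.9-5.1% for every test, so all are valid.

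**Effect at Week 6 only, v = (1, 0).** The 2-df interaction has 70.9/75.2/79.0% at r = 0.5/0.65/0.8; the Week 12 contrast has 5%.

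**The case against.** **The planned test is valid, and different trajectories are a fair question for a pilot.** This stands. The interaction also detects an effect seen only at Week 6, which the Week 12 contrast does not. For a steady effect, a joint 2-df test of both visits adjusted for baseline would have 85-88%, more than the Week 12 contrast. The case for Week 12 is that it matches the treatment period and gives an estimate, not that it is the most powerful test for every pattern.

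**The correlations may be higher than 0.5-0.8.** Section 5.3 gives a baseline ALT of 130 ± 63 U/L and changes of -20 ± 10 and -30 ± 8 U/L. If the ± values are SDs and variances are equal, r = 1 - 10²/(2 × 63²) = 0.987, or 0.992 with 8. The plan's own 10% SD, about 13 U/L at a mean of 130, gives 1 - 13²/(2 × 63²) = 0.979. Over that range a steady effect has about 83%, the two-visit test nearly 80%, and only a gradual effect loses (about 70-71%). The documents do not say that the ± values are SDs, and they concern ALT only. Still, the loss for ALT could be small.

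**Few outcomes clearly have three visits.** Laboratory work is called fasting at Weeks 0 and 12 but not at Week 6 (Sections 3.9, 4.1, 4.3). The clear three-visit cases are BMI z-score, waist and absolute ALT, and ALT already has its own Week 12 comparison. This limits the omnibus point. Two-visit outcomes still lack baseline adjustment.

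**ANCOVA is already allowed, and its assumptions are to be checked.** True, but it is an option with covariates chosen later. No sentence names the baseline value, age group or Week 12.

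**Stronger readings that a reader might infer.**

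- That the interaction has almost no power for a sustained benefit. This would follow if Week 0 were a covariate or subtracted, since the test would then compare Week 12 with Week 6: 5% for a steady effect, about 23-27% for a gradual one at r = 0.5-0.8. The PROMIS example and the wording on time points disfavour that reading, so those figures should not carry the point.
- That nothing is estimated unless the interaction is significant. Section 5.4 makes only the post-hoc tests follow a significant interaction. The adjusted means and intervals carry no such condition, though they are not said to be arm differences.

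**Conclusion.** The point holds as an inexpensive improvement, not as an error in the plan. For continuous secondary outcomes, the named main mixed-model test is an interaction, and no text fixes a Week 12 arm difference adjusted for the baseline value and age stratum.

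Against 80% for that difference, and with equal correlations of 0.5-0.8 and complete data, the planned test has about 71-79% (steady) or 58-66% (gradual) with three visits, and 68-76% with two. At r of about 0.9 or more, the steady-effect loss disappears and the two-visit loss is 2 points or less; a gradual effect stays near 68-71%. The correlations are assumed, so these figures show direction and rough size only. The reach is limited to secondary outcomes; the primary ALT test and its sample size do not change.

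**What to change.** For each continuous secondary outcome, make the main result the Week 12 arm difference with its 95% confidence interval, adjusted for the baseline value and the age group used in randomisation:

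- **Weeks 0 and 12 only** (glucose tolerance test, MRI, PROMIS): ANCOVA on the Week 12 value.
- **Weeks 0, 6 and 12** (BMI z-score, waist, absolute ALT): a mixed model on the Week 6 and Week 12 values with baseline value, age group, visit, arm and visit-by-arm, from which the Week 12 difference is taken.

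Report it whether or not the interaction is significant. Keep the time-by-arm interaction and the Week 6 difference as supportive, and state the role of Week 0 and the coding of time for that interaction. Align the Synopsis and both parts of Section 5.4 so that each outcome has one named main method. In doing so, drop percent change for BMI z-score, where that scale has no useful meaning.

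The cost is a few sentences, with the same data, visits and model family. The downside is that an effect present only at Week 6 would appear only in the supportive analysis, and the test of overall time pattern would no longer lead.
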